Home-based tDCS for behavioral symptoms in Alzheimer's disease and related dementias

NCT05478681

Version Date: 08/27/2024

Protocol Title: Home-based tDCS for behavioral symptoms in Alzheimer's disease and related dementias

Principal Investigator: [name], PhD, UTHealth

Co-Investigators:

[name] [name], UT Health San Antonio

[name] [name], UT Health San Antonio

[name], UTHealth

[name], UTHealth

General Information

Study Title	Home-based tDCS for behavioral symptoms in Alzheimer's disease and related dementias (ADRD)	
Short Title	tDCS for behavioral symptoms in ADRD	
Study Design	
This is an open-label, non-randomized clinical trial to assess acceptability, safety and efficacy of providing transcranial direct current stimulation (tDCS) to Alzheimer's disease and related dementia (ADRD) patients with behavioral symptoms.
 
All participants will receive active tDCS with a constant current intensity of 2mA for 30 minutes, five times per week, for six weeks. Anodal tDCS will be applied to the left dorsolateral prefrontal cortex, while cathodal electrode will be positioned on the right dorsolateral prefrontal cortex. Caregivers will set up and administer tDCS for participants with AD at home. All sessions will be remotely supervised by trained research staff through video conferencing software. Participants will be assessed at baseline, treatment day 12, treatment day 28, treatment day 42, and 6 weeks
	

	post-treatment.	
Study Participants	Patients with ADRD and behavioral symptoms will be recruited at the UTHealth Neurosciences Neurocognitive Disorders Center ([name]), and UT Physicians Center for Healthy Aging ([name]).	
Planned Sample Size	20	
Planned Study Period	12 weeks	
	Objectives	Outcome Measures
Primary Goal	To assess acceptability, and safety of providing tDCS to ADRD patients with behavioral symptoms.	Acceptability will be evaluated using Likert scale (from 0 [strongly disagree] to 10 [strongly agree]) to answer ten affirmatives regarding the use of home-based tDCS. Safety will be assessed with a questionnaire about side effects that include itching, burning, headache, fatigue, and dizziness.
Secondary Goal	To assess the efficacy of tDCS for ADRD-related symptoms, mainly behavioral symptoms.	Behavioral and cognitive symptoms will be evaluated through validated clinical instruments.

Background Information

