We will target the stimulation on the dorsolateral prefrontal cortex based on the facts that prior studies showed positive results with this strategy for behavioral and cognitive symptoms of other neuropsychiatric disorders (17-19). According to previous home-based tDCS protocols (20, 21), all sessions will be remotely supervised by trained research staff (RA), therefore, the sessions will run from Monday through Friday for four consecutive weeks. The remote supervision of the sessions will be possible through video conferencing software (e.g., WebEx), and will ensure the use of proper technique and compliance to the study schedule, also monitoring any adverse events. The device (tDCS) will be programmed and cannot be tampered. Participants will be assessed at baseline, treatment day 14, treatment day 28, treatment day 42- and 6-weeks post-treatment (Fig.1). The device will be delivered to patients at baseline and will be returned at the end of the treatment (week 6).

Sample size

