frequentist analyses) and are less influenced by multiple comparisons in general due to observation of the Likelihood Principle. The current Bayesian analyses stipulate posterior probabilities ≥ 0.75 (equivalent to a Bayes factor = 0.33 or 3.0) that parameter estimates are greater or less than zero provide a minimum threshold of evidence to emphasize the value in discerning effects in a small study. The Bayesian inferential paradigm can provide probabilistic estimates of effects irrespective of sample size. Power considerations focus on identifying change over time from baseline to end-of-treatment. Notably, the Bayesian analyses will provide the primary inferential results; thus considerations for the frequentist analyses are limited by the small sample size and provided solely as due diligence. Given alpha = 0.05, a sample size N = 20 provides 80% power to detect an effect size Cohen's d = 0.66.

Study Population

A maximum of 20 persons with ADRD and clinically-meaningful behavioral symptoms will be enrolled in the study. This sample size is set to maximize the number of participants that may be enrolled over the time period of the proposal assuming a credible average recruitment rate, given the financial resources.

Inclusion criteria. Participants who are 60 years or old will be considered eligible if they: (1) have ADRD and clinically-meaningful behavioral symptoms, (2) have a caregiver willing to participate in the study, (3) can speak and read English, (4) have stable doses of medications for at least one month. The diagnosis of ADRD will be verified by the investigators based on Mini-Mental Status Exam score (between 14 - 25) (22, 23). Clinically-meaningful behavioral symptoms will be determined by the Neuropsychiatric Inventory (NPI), and defined as a total score ≥ 10 arising from at least two domains (24, 25).

Exclusion criteria. Participants will be excluded if they have: (1) any unstable concurrent medical conditions, (2) history of brain surgery, seizure, or intracranial metal implantation, (3) current alcohol/substance use disorder.

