Recruitment and Retention. Participants will be recruited at the *UTHealth Neurosciences Neurocognitive Disorders Center* ([name]), *UT Physicians Center for Healthy Aging* ([name]), and at the UT Health San Antonio's Glenn Biggs Institute for Alzheimer's and Neurodegenerative diseases Neurology clinic ([name]). Study flyers with summary and contact information about the study will be used at the *UTHealth Neurosciences Neurocognitive Disorders Center* as a mean to provide awareness and information to potential participants. Flyers will be available at the request of potential subjects at the moment of their visit with [name], and at dedicated spaces for research recruitment material in the *UTHealth Neurosciences Neurocognitive Disorders Center*. As serious adverse effects and problems with the device use are not anticipated, it is expected a high retention rate. The remote supervision of the tDCS or sham daily sessions by trained research staff will contribute to the retention of subjects during the trial.

Training plan. Patients will be instructed on treatment at baseline, when they will

receive the device. A trained research staff will instruct the participant's caregiver on how to handle the equipment. All sessions will be remotely supervised by trained research (RA) staff, who will be able to answer questions during the sessions and verify that the device is being used correctly.

Study Procedures

Primary Outcome

Acceptability will be evaluated using the method proposed by Ahn et al. (2019) (21). Participants and/or their caretakers will be asked to apply a Likert scale (from 0 [strongly disagree] to 10 [strongly agree]) to answer ten affirmatives regarding the use of home-based tDCS. For example, question 1: It was easy to prepare the device and accessories, question 7: I felt confident using the device. Overall acceptability across groups will be evaluated by descriptive measures of satisfaction ratings. We expect that participant satisfaction ratings at the end of treatment will demonstrate high acceptance of tDCS treatment in the present sample. Acceptability scale will be applied on Week 2, 4, 6 and 12.

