Safety will be assessed with a questionnaire about side effects that include itching, burning, headache, fatigue, and dizziness (21). The most common side effects of tDCS reported in the literature are very mild and include tingling, burning sensation, and skin redness, while other less common side effects may include headache, sleepiness, dizziness, and difficulty concentrating (22-23). Although rare, a possible adverse event of tDCS is the occurrence of skin lesions or small skin burns on the site where electrodes touch the skin (24-25). The side effects questionnaire will be applied on Week 2, 4 and 6 to assess the incidence and frequency of side effects in our recruited sample. We expect that the occurrence of side effects will be similar to the frequencies reported in the scientific literature, demonstrating that home-based tDCS is a safe and feasible intervention to be used on the management of ADRD patients with behavioral symptoms.

Secondary Outcome

The main efficacy measure will be change on the Neuropsychiatric Inventory (NPI) score (26), the best-validated tool for measuring NPS in dementia patients. This 12-item informant-based interview is a widely accepted measure of NPS in dementia. The NPI consists of a detailed evaluation of the following 12 neuropsychiatric domains: hallucinations, delusions, agitation/aggression, depression, anxiety, irritability, disinhibition, euphoria, apathy, aberrant motor behavior, change in night-time sleep behavior, and changes in appetite and eating (27). Each NPS domain is rated according to its severity (0-3) and frequency (0-4) (28). NPS will be assessed at baseline, during treatment (weeks 2, 4 and 6) and 6 weeks post-treatment. Our hypothesis is that patients receiving tDCS will demonstrate lower NPI scores at the end of treatment.

Other clinical outcome measures will include: (1) total score on the Brief Dimensional Apathy Scale (bDAS) (29); (2) depressive symptoms as assessed by the

Cornell Scale for Depression in Dementia (CSDD) (30); (3) cognition as evaluated by the Mini-Mental State Examination (MMSE), which includes memory, language, praxis and orientation tasks, yielding a global cognition score ranging 0 to 30, with higher scores indicating better performance (31). Our hypothesis is that all participants receiving treatment will demonstrate lower scores on the bDAS and CSDD, and higher scores on the MMSE at the end of treatment.

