Potential Benefits to Research Participants. If our hypothesis is correct, all subjects might benefit from the study participation. Importantly, the results will be relevant to the field of AD and neuromodulation.

Significance

Our proposal will address a frequent and sometimes overlooked clinical problem in patients with ADRD, i.e. behavioral symptoms. The proposal can advance the field of non-pharmacological strategies for NPS, also presenting a great potential for clinical translation. Home-based intervention with real-time monitoring through a secure conferencing platform is a new modality for improving symptom management in ADRD. Moreover, home-based, remotely supervised tDCS has advantages over clinic-based sessions, considering the time and cost associated with attending multiple sessions over several days. Caregivers will be trained at the in-person baseline visit, and all the tDCS sessions will be remotely supervised via secure videoconferencing software by trained research staff for the entire duration of each session to ensure the use of proper technique and to monitor any adverse events.

Costs and Compensations

Participants will not be charged for tests, procedures or other costs incurred solely for the purposes of this research. Patients will receive a voucher of US 50.00 for their time dedicated to each evaluation (total number of assessments = 5).

Publication Plan

This study will represent an original contribution to the areas of non-pharmacological approaches for NPS in ADRD and neuromodulation. The results will be presented in national and international meetings, and published as a research manuscript.

References

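### The primary safety outcome rests on a fortnightly questionnaire with no stated respondent or recall window, and nothing says side effects noted at the supervised sessions are counted

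*Combined protocol and SAP*

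**What the plan says.** Study Procedures, Primary Outcome, defines the measure: "Safety will be assessed with a questionnaire about side effects that include itching, burning, headache, fatigue, and dizziness". The same paragraph sets timing and purpose: "The side effects questionnaire will be applied on Week 2, 4 and 6 to assess the incidence and frequency of side effects". It expects occurrence to resemble published frequencies and takes that as showing the treatment to be safe and feasible at home. Table 1 marks the questionnaire as a primary outcome and lists no other safety collection.

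The inclusion criteria verify the diagnosis "based on Mini-Mental Status Exam score (between 14 - 25"; the Secondary Outcome section notes that this instrument includes memory tasks.

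The General Information table gives treatment "five times per week, for six weeks". Study Design says instead that "the sessions will run from Monday through Friday for four consecutive weeks".

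For acceptability, the respondent is named: "Participants and/or their caretakers will be asked to apply a Likert scale". The side effects paragraph has no such sentence.

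Two safeguards are described. Under Significance, sessions are "remotely supervised via secure videoconferencing software by trained research staff for the entire duration of each session", partly to watch for adverse events; Study Design says much the same. The Ethics section requires a caregiver or relative at assessments and sessions so that information is reliable.

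**The concern.** The outcome is meant to give both how many patients are affected and how often. The named items are mostly felt by the patient and not readily seen, and many episodes will be mild and short. A questionnaire every two weeks is a weak instrument for a count over some ten sessions, more so where memory is impaired. A caregiver who answers instead can report only what was voiced or visible, and would also be summarising about ten sessions.

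Staff are on a video call at every session, so same-day information is within reach. Nothing in the plan says that staff go through the items, record the answers on a form, or feed them into the primary outcome.

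At stake is the safety conclusion itself. The trial has one arm, so there is no concurrent group measured in the same way against which a collection loss would cancel. Under-counting would move the result towards the reassuring reading that the plan expects.

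**Working it through.** **The plan's own figures.** The plan gives no side effect rate and no recall accuracy. Its only power figure (80% at N = 20, d = 0.66) concerns change in efficacy scores and has no bearing here.

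**Exposure behind each questionnaire.**
- Six-week schedule: 5 × 6 = 30 sessions, and 5 × 2 = 10 per two-week interval.
- Four-week wording: 5 × 4 = 20 sessions, so the Week 6 questionnaire would follow an interval with none.
- The first on-treatment assessment is on day 12 in the General Information table and on day 14 in Study Design.

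**Effect of recall.** Let q be the share of sessions with a given effect and r the probability that an occurrence is reported at the questionnaire. Assume q is the same for all patients and sessions are independent. Both q and r are assumptions. Over ten sessions:
- truly ever affected = 1 − (1 − q)^10
- recorded as ever affected = 1 − (1 − qr)^10
- sessions affected = 10q true, 10qr recorded

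| q | True ever affected | Recorded, r = 0.7 | Recorded, r = 0.5 | Recorded, r = 0.3 |
|---|---|---|---|---|
| 5% | 40% | 30% | 22% | 14% |
| 10% | 65% | 52% | 40% | 26% |
| 30% | 97% | 91% | 80% | 61% |
| 50% | 99.9% | 99% | 94% | 80% |

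Example: q = 10%, r = 0.5 gives 1 − 0.95^10 = 40%, against 1 − 0.90^10 = 65%. In 20 patients that is about 8 recorded instead of 13. At q = 30% it is about 16 instead of 19.

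Frequency falls by the factor r whatever q is: at q = 30% and r = 0.5, from 3.0 to 1.5 sessions in ten. The share ever affected is hit mainly for infrequent effects, because a patient counts once any single occurrence is reported.

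**Limiting cases.** If an effect occurs about once per affected patient, the share affected also falls by the factor r: a true 30% (6 of 20) gives 5.4, 4.2 or 3.0 expected reporters at r = 0.9, 0.7 or 0.5. If every occurrence is captured (r = 1), nothing is lost.

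**Would sampling a few sessions do?** Suppose the items were asked only at the last session before each assessment, 3 of 30 sessions. With q = 10% and perfect capture, the share ever affected is 1 − 0.9^3 = 27%. The truth over 30 sessions is 1 − 0.9^30 = 96%, and two-week recall at r = 0.5 would record 1 − 0.95^30 = 78.5%. Sampling would therefore do worse than recall for ever-incidence unless r fell below about 0.10 (from 1 − 0.1r = 0.9^(1/10)). The items have to be asked at every session.

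**The case against.** The strongest reply is that the plan never says patients must recall ten sessions. It gives the timing only. The instrument comes from a cited home-based tDCS trial in knee pain, and its wording is not in the documents; it may ask about current symptoms or the latest session. A caregiver who attended the sessions must be at each assessment, and staff watch every session for adverse events. This much stands: a reader might infer that under-reporting is certain, or that cognitively impaired patients are the sole source, and the documents support neither. They leave respondent and window open, which is a gap in a primary outcome, and they do not connect the two safeguards to that outcome.

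A reader might also infer that the error can run only one way. It need not. Headache, fatigue and dizziness occur without stimulation, and with no sham arm a two-week checklist may attribute background symptoms to treatment. Headache and fatigue can also outlast a session, and fatigue can be seen. Forgetting lowers the count, but the net direction is not proven.

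It is tempting, too, to multiply a patient-level rate by a recall share, so that 50% to 80% recall turns 30% into 15% to 24%. That holds only for effects occurring about once per patient.

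Finally, with a Monday start, days 14, 28 and 42 are Sundays, two days after the last weekday session. But day 12 would be a Friday, a session day, and the four-week wording changes the picture again. The point does not rest on the calendar.

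**Conclusion.** The concern holds as a conditional one. The only scheduled collection for a primary outcome of incidence and frequency is a questionnaire at three time points, with respondent, recall window and link to the supervised sessions all unstated. If it works by two-week recall, frequency will be under-counted in proportion to recall, and ever-incidence mainly for infrequent effects: at an assumed 50% recall over ten sessions, 65% becomes 40% at q = 10% and 97% becomes 80% at q = 30%. These figures rest on an assumed recall, assumed effect rates, independent sessions and the six-week schedule. If the instrument or its respondents capture everything, the loss is zero. The documents do not establish that tDCS will look safer than it is. They show that the plan cannot exclude this, while a better source is available on calls that staff already attend. The plan should be changed on this point.

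**What to change.** 1. At the end of every supervised session, on the existing video call, staff ask the patient each named item and record the answers on a short form, with the caregiver's observations in a separate field.
2. Base the primary safety outcome on these records: incidence as the share of patients ever affected, frequency as the share of sessions affected.
3. Keep the Week 2, 4 and 6 questionnaire as a separately reported supplement, which also catches effects that begin after the call. State its respondent and recall window.
4. Reconcile the six-week and four-week session schedules, and day 12 with day 14, since they set the exposure behind each questionnaire.

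Cost: protocol wording, a form, data entry and about a minute per call (assumed). Over 30 calls and 20 patients that is 600 minutes, or 10 hours of staff time; over 20 calls, 400 minutes. No visit is added. The recorded incidence will probably rise, and some of the rise may be background symptoms, which neither method can separate without a control arm.

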The sample of this study consists of 20 older adults aged 60 years-old and over with ADRD and behavioral symptoms. Study participants or their legally authorized representatives will give informed consent. Moreover, caregivers and/or relatives will be required to be present during the clinical assessments and tDCS sessions to ensure reliable information and proper use of the device. Participants will be recruited without any specific regard to sex, race, religion or ethnicity. Patients will be recruited at the UTHealth Neurosciences Neurocognitive Disorders Center, and UTHealth Center for Healthy Aging. We will recruit ADRD patients whose dementia is of mild to moderate severity. Adults younger than 60, adolescents and children are excluded as we are focusing on dementia, an age-related disorder that usually affects individuals aged 60 and older. No other special classes of vulnerable individuals will be included. It is anticipated that the subject demographic profile will mirror the larger population of individuals with ADRD from which they are recruited.

Informed Consent and Assent. Potential subjects and their caregivers/relatives will be informed about the study purpose, procedures, risks and benefits. They will be informed that participation in the research study is voluntary and that they are free to decline to be in the study, or to withdraw from it at any point. Study records will be kept confidential. Study information will be coded, and only study personnel will have access to the files.

Protection Against Potential Risks. The risks to the subjects involved in this study are minimal. To ensure this, we will take necessary steps to reduce risk for all study participants. We will try to create an atmosphere of security and trust prior any clinical assessment in order to minimize any discomfort with the research questions. In addition, subjects are always given permission to not answer questions with which they feel uncomfortable. A number of procedures (e.g. use of identifying numbers instead of names) will be implemented to protect subjects against loss of confidentiality. Side effects related to active tDCS application are uncommon, and mild when present, including: itching and burning sensation on the scalp, mild headache, dizziness, and fatigue. Although rare, a possible adverse event of tDCS is the occurrence of skin lesions or small skin burns on the site where electrodes touch the skin (24-25).

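### The primary safety conclusion is planned on how often side effects occur; no severity rating or summary is stated, so it can address whether they are uncommon but not whether they are mild

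*Combined protocol and SAP*

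**What the plan says.** The Objectives table and Table 1 make the side effects questionnaire a primary outcome, applied at Weeks 2, 4 and 6. It covers itching, burning, headache, fatigue and dizziness, and is cited to an earlier home-based tDCS pilot in knee osteoarthritis. Study Procedures, Primary Outcome, gives its purpose as "to assess the incidence and frequency of side effects in our recruited sample". The conclusion follows from occurrence: "We expect that the occurrence of side effects will be similar to the frequencies reported in the scientific literature", and this is said to demonstrate a safe and feasible intervention.

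Severity appears only in descriptive text. The same section says "The most common side effects of tDCS reported in the literature are very mild". The paragraph on protection against potential risks, in the ethics section, says "The risks to the subjects involved in this study are minimal" and "Side effects related to active tDCS application are uncommon, and mild when present". Both places also name a physical injury, described as rare: "a possible adverse event of tDCS is the occurrence of skin lesions or small skin burns on the site where electrodes touch the skin".

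Study Design and Significance say that sessions are supervised by video and watched for adverse events. Neither describes grading. Data and Safety Monitoring covers de-identification, storage and publication. Statistics sets out a modelling framework but names no safety endpoint.

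**The concern.** The route from data to conclusion has one step: count who reports an effect and how often, compare with published frequencies, and call the treatment safe if they are similar. Intensity does not enter. The risk statement, by contrast, depends on effects being both uncommon and mild.

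This matters because caregivers deliver the stimulation at home to people with dementia, and there is no control arm. A faint itch and a painful burning sensation that ends a session would each be one occurrence in the result as described. Readers of the final report will want to know how bad the effects were as well as how many there were, and the plan does not commit to telling them.

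**Working it through.** The plan gives no figure for safety. Its only design calculation (N = 20, 80% power, d = 0.66) concerns change from baseline to end of treatment. It reproduces at 79.9% with a paired t-test on 19 degrees of freedom, two-sided alpha 0.05, and has no bearing here.

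**Step 1. Match each claim to the planned measure.**

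| Claim in the risk statement | Planned measure that could address it | Stated? |
|---|---|---|
| Side effects are uncommon | Incidence and frequency from the questionnaire | Yes |
| Side effects are mild when present | An intensity rating and a summary of it | No |
| Skin lesions or small burns are rare | A skin-injury item; the nearest listed item is burning, a sensation | No |

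**Step 2. Check whether another section fills the gap.** Live supervision could bring a severe event to notice, but no grading scale, recording rule or summary carries it into the primary safety result. Data and Safety Monitoring and Statistics are silent on severity. Elsewhere the protocol does describe graded measurement: each NPI domain is rated 0-3 for severity and 0-4 for frequency, and acceptability has a 0-10 agreement scale.

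**Step 3. Show what the missing grade would provide.** The input from the documents is n = 20. The counts x below are assumptions for illustration, as the documents give no expected rates. The exact (Clopper-Pearson) two-sided 95% limits are

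- lower = Beta quantile(0.025; x, 20 − x + 1), taken as 0 when x = 0
- upper = Beta quantile(0.975; x + 1, 20 − x)

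| Participants with the effect | Proportion | Exact 95% CI |
|---|---|---|
| 8 of 20 | 40% | 19.1% to 63.9% |
| 1 of 20 | 5% | 0.1% to 24.9% |
| 0 of 20 | 0% | 0% to 16.8% |

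The last limit can be checked by hand: 1 − 0.025^(1/20) = 0.168.

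If 8 of 20 report burning, an occurrence-only result is the first row whether all eight are mild or all eight severe. With grades, the first case adds the third row for severe burning, and the second case repeats the first row for severe burning. The two situations then look different.

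**Step 4. Chance of seeing a severe effect at all.** P(at least one in 20) = 1 − (1 − p)^20. For assumed true rates of 1%, 5% and 10% this is 18%, 64% and 88%. A trial of this size can detect a fairly common severe effect but cannot rule out an uncommon one.

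**The case against.** The strongest objection is that the form is not in the documents. It is taken from an earlier study and may already ask about intensity. A reader might infer that severity will not be recorded, or that the trial would be unaware of a painful or injurious event. The documents do not support that. They leave open what the form records, research staff supervise each session for its entire duration, and a caregiver or relative must be present. This part of the objection stands: the gap is in what the plan states and uses, and may not be in what is collected. It does not close the gap, because the stated purpose and the stated basis for the conclusion are occurrence only, so any grades collected would have no planned role.

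A second objection is that the wording about mild effects is a literature description and a pre-study ethics statement, and not a hypothesis the trial promises to test. That is also fair. A reader might infer that the risk statement rests on mildness alone, or that the protocol contradicts one of its own aims. Neither holds: the statement rests on effects being uncommon as well as mild, and the planned measure addresses the first. What remains is that the trial would declare the intervention safe on half of the argument used to justify its risk.

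Third, the counts above are illustrative, and 20 participants give wide limits even with grading. This is true. It limits what a severity summary can show, but the summary would still be informative and costs little.

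**Conclusion.** The point holds as a gap in the stated safety analysis. As planned, the primary safety conclusion rests on occurrence resembling published frequencies and would be the same at any intensity. It can address whether side effects are uncommon but not whether they are mild. The plan yields no stated estimate for moderate or severe effects; with grading, 0 of 20 severe would support an upper 95% limit of 16.8%, and 1 of 20 an interval of 0.1% to 24.9%.

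This rests on the text of the protocol alone. If the form already rates intensity, the remedy reduces to stating the scale, how it will be summarised and how it enters the conclusion. The intervals assume that all 20 participants are enrolled and contribute data. The trial can run without this change, but its safety statement would be weaker than it needs to be.

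**What to change.** 1. Say whether the questionnaire rates intensity. If it does, name the scale and its categories.
2. If it does not, add to each item a mild/moderate/severe rating with written definitions. The 0-10 acceptability scale should not be borrowed, since it measures agreement and has no cut-off for moderate.
3. Add a yes/no box to each item for whether a session was interrupted. This only records what happened and sets no rule for when to interrupt.
4. Add an item for skin lesions or burns, which the protocol itself names as a possible harm.
5. Report for each item the number and proportion of participants with any effect, with a maximum severity of moderate or worse, and with a maximum severity of severe, each with an exact 95% CI. Count participants, taking the worst grade over Weeks 2, 4 and 6. The up to 20 × 3 = 60 questionnaires are not independent.
6. Reword the safety expectation so that the conclusion rests on both occurrence and severity.

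The cost is a column and an item on an existing form, a short amendment and about a minute more per visit. The drawback is imprecision: at n = 20 the severity intervals will be wide and should be reported as such.
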